**Table JPBQ.12.2. Properties of Design for Progression-Free Survival**

Information Fraction	Cumulative Events	Cumulative Alpha Spent	Cumulative Beta Spent	Boundary Reject $H_0$ (1-sided p-value)
0.70	119	0.0082	0	<0.0082
1	170	0.0250	0.2	<0.0223

The actual alpha spent will be calculated based on the actual number of events observed at the time of analysis using software that implements the alpha-spending function noted above (eg, ADDPLAN 6.0 or SAS 9.2).

If the interim analysis crosses the boundary of significance at the pre-specified level, the study is considered positive. If statistical significance is not declared at the interim, the final PFS analysis will be conducted with approximately 170 PFS events. All remaining alpha will be spent at the final analysis on Cohort A. Once statistical significance is declared at either interim analysis or the final analysis, the study is considered positive.

The Cox proportional hazard model (Cox 1972) with treatment as a factor will be used to estimate the hazard ratio and corresponding 95% CI with Wald's test p-value after stratifying for the same randomization variables specified for the primary analysis.

### **12.2.7. Secondary Outcomes and Methodology**

The secondary objectives of the study are listed in Section [6.2](#).

#### **12.2.7.1. Progression-Free Survival in Cohort B**

Progression-free survival in Cohort B is the key secondary endpoint for this study. The measurement, rules of censoring, and analysis methods of PFS in Cohort B are the same as those of PFS in Cohort A. Only if statistical significance is declared at the Cohort A interim analysis,

the interim analysis of Cohort B will be conducted based on the same data cutoff. No alpha specified for interim of Cohort B. If patients in Cohort A continue being followed for PFS until final analysis, the final analysis of Cohort B will be conducted at the same time of Cohort A final analysis. If Cohort A stops early at interim due to efficacy, the final analysis of Cohort B may be conducted after approximately 105 PFS events have been observed in Cohort B (that is, an approximately 30% censoring rate).

#### **12.2.7.2. Overall Survival**

Overall survival will be analyzed for each cohort. Overall survival time is measured from randomization until death from any cause. Patients who are alive will be censored at the data cut-off date of study completion. The final analysis of OS will be conducted together with the analysis of PFS at study completion.

Overall survival will be analyzed using the Kaplan-Meier method and the Cox proportional hazard model.

#### **12.2.7.3. Objective Response Rate, Disease Control Rate, Clinical Benefit Rate, and Duration of Response**

For each cohort, the objective response rate, DCR, and CBR of each treatment arm will be calculated as defined in Section 10.1.4 using the ITT population. All rates will be compared between treatment arms within the cohort based on a normal approximation for the difference between the rates.

The DoR time is defined only for responders (patients with a best response of CR or PR). It is measured from the date of first evidence of CR or PR to the date of objective progression or the date of death due to any cause, whichever is earlier. A Kaplan-Meier analysis of DoR will be performed to estimate the DoR curve for each arm in each cohort.

#### **12.2.8. Sensitivity Analysis**

Sensitivity analyses will be undertaken for calculation of the primary endpoint in order to evaluate the robustness of the analysis. Details can be found in the SAP.

#### **12.2.9. Pharmacokinetic and Pharmacodynamic Analyses**

Pharmacokinetics analyses will be conducted on all patients who have received at least 1 dose of study treatment and have had samples collected (see PK sampling schedule in [Attachment 7](#)).

Mean population PK parameters for abemaciclib and its metabolites in plasma (clearance, area under the plasma concentration versus time curve [AUC], volume of distribution, and half-lives) and inter-individual PK variability will be computed using nonlinear mixed-effect modeling implemented in NONMEM. Covariate effects (such as age, weight, sex, creatinine clearance, and plasma protein levels) on the PK parameters of abemaciclib and its metabolites in plasma will also be investigated.

Likewise, and if warranted by the data, mean population PK parameters for anastrozole, letrozole, or fulvestrant in plasma and inter-individual variability estimates will also be computed using nonlinear mixed-effect modeling implemented in NONMEM.

Finally, potential pharmacodynamic data (such as neutrophils, lymphocytes, or platelet counts in blood) collected in this study may be analyzed by means of NONMEM and connected to the population PK model for abemaciclib and/or NSAID or fulvestrant in a PK/PD model. Also, CTS associated with PFS and OS may be analyzed for exploratory objectives.

### **12.2.10. Biomarker Analyses**

Correlative analyses may be performed to investigate associations between biomarkers and clinical endpoints as deemed appropriate.

### **12.2.11. Health Outcome/Quality-of-Life Analyses**

Patient-reported outcomes are measured through paper versions of the following:

- EORTC QLQ-C30
- mBPI-sf

For each patient with data from baseline and at least 1 post-baseline visit, the maximum change from baseline score will be calculated and summarized for EORTC scale scores and mBPI-sf “worst pain.” The reason and number of missing and incomplete questionnaires/assessments by visit will be summarized for each instrument and study arm.

Further analysis details will be described in the SAP.

#### **12.2.11.1. Health-Related Quality of Life**

European Organization for Research and Treatment of Cancer Quality of Life Questionnaire-Core 30 instrument data will be scored as described by Aaronson and colleagues (Aaronson et al. 1993). If not already addressed in the EORTC scoring manual (Fayers et al. 2001), descriptive statistics for each EORTC QLQ-C30 item will be calculated. Descriptive statistics will be calculated for each dimension and the total score for each treatment arm in a cohort.

#### **12.2.11.2. Pain Intensity**

Individual pain items on the mBPI-sf (ie, worst, least, average, and current pain) will be described using descriptive statistics (eg, n, mean, median, standard deviation, minimum, and maximum) by treatment arm and time points. A mixed effects model, repeated measures model may be applied to compare between treatment arms, which may be adjusted for other covariates. Corresponding analyses will also be conducted for the mean of 7 pain interference with function items. If a patient does not complete Questions 5a through 5g on the mBPI-sf, the mean score for the 7 pain interference items will be calculated based on those answered questions when at least 4 out of 7 questions were completed (ie,  $\geq 50\%$  of the questions were answered). Separate similar analyses will be conducted using the average of the mBPI-sf/worst pain assessments associated with each cycle.

Pain analysis will be based on all randomized patients with at least 1 baseline mBPI-sf “worst pain” and 1 mBPI-sf “worst pain” score on Cycle 2 Day 1 or later.

The mBPI-sf will be administered at baseline prior to study drug dosing and the Cycle 1, Day 1 score will be treated as a baseline observation and the Day 1 score of each subsequent cycle will be attributed to the previous cycle. The mBPI-sf will be administered at treatment discontinuation and grouped with observations from the previous cycle.

Time to worsening in pain will be described using the Kaplan-Meier method and will be made between the 2 treatment arms by a log-rank test. “Worsening” will be defined as either a “worst pain” increase of  $\geq 2$  points postbaseline or an analgesic drug class increase of  $\geq 1$  level. Worsening rate at Years 1, 2, and 3 will be estimated and compared between the 2 treatment arms within each cohort. The number of events due to each criterion will be described.

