#### **9.4.1.1.4. Nonhematologic Toxicity**

If a patient experiences Grade  $\geq 3$  nonhematologic toxicity, then dosing must be suspended (until the toxicity resolves to either baseline or at least Grade 1) and the dose of blinded study drug must be reduced as outlined in [Table JPBQ.9.3](#).

If a patient experiences persistent or recurrent Grade 2 nonhematologic toxicity (except diarrhea; see Section 9.4.1.1.4.1 or ALT increased, refer to Section 9.4.1.1.4.2 ) possibly related to blinded

study drug that does not resolve with maximal supportive measures within 7 days to either baseline or Grade 1, then dosing must be suspended (until the toxicity resolves to either baseline or at least Grade 1) and the dose of blinded study drug must be reduced by 1 dose level as outlined in [Table JPBQ.9.3](#).

Before re-initiation of blinded study drug, nonhematologic toxicity (except alopecia and fatigue) must resolve to either baseline or at least Grade 1.

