#### 10.2.1.1. Health-Related Quality of Life

Broadly used in cancer trials, validated, and available in over 80 different languages, the EORTC QLQ-C30 (Aaronson et al. 1993) is a reliable and validated tool that has supported quality-of-life text in the European Medicines Evaluation Agency labels. The EORTC QLQ-C30 self-reported general cancer instrument (Aaronson et al. 1993) consists of 30 items covered by 1 of 3 dimensions:

- global health status/quality of life (2 items)
- functional scales (15 total items addressing either physical, role, emotional, cognitive, or social functioning)
- symptom scales (13 total items addressing either fatigue, nausea/vomiting, pain, dyspnea, insomnia, appetite loss, constipation, diarrhea, or financial impact)

The EORTC QLQ-C30 questionnaire is administered per the Study Schedule ([Attachment 1](#)). The recall period is the past week, completion time is typically 5 to 7 minutes, and the questionnaire will be scored as described by the European Organization for Research and Treatment of Cancer (EORTC) scoring manual (Fayers et al. 2001). The EORTC population will include all patients who completed at least 1 baseline assessment followed by at least 1 EORTC assessment after 1 dose of study drug.

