Abbreviations: BL = baseline; BP = blood pressure; CT = computed tomography; CTCAE = Common Terminology Criteria for Adverse Events; ECG = electrocardiogram; ECOG = Eastern Cooperative Oncology Group; EORTC QLQ-C30 = European Organization for Research and Treatment of Cancer Quality of Life Questionnaire-Core 30; FSH = follicular stimulating hormone; HR = heart; IV = intravenous; mBPI-sf = modified Brief Pain Inventory short form; MRI = magnetic resonance imaging; NSAI = nonsteroidal aromatase inhibitor; PD = progressive disease; PK = pharmacokinetics; Q12H = every 12 hours; Q24H = every 24 hours; RECIST = Response Evaluation Criteria in Solid Tumors; RR = respiratory rate; SAE = serious adverse event; temp = temperature.

- a Short-term follow-up begins the day after the patient and the investigator agree that the patient will no longer continue study drug and lasts approximately 30 days ( $\pm 7$  days); the associated study procedures are performed once at the end of this period. Long-term follow-up begins the day after short-term follow-up is completed and continues until the patient's death or overall study completion; the associated study procedures are performed approximately every 12 weeks ( $\pm 14$  days) for the duration of this period.
- b For Cycle 2 and beyond, the start of a cycle may be delayed up to 7 days for logistical reasons and up to 14 days to allow sufficient time for recovery from toxicity possibly related to a study drug. Refer to Section 9.4.1.1.2.
- c Informed consent form is signed within 28 days prior to randomization of study drug and prior to performance of any protocol-specific tests/procedures.

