NSAI and blinded study drug at home at least 4 hours prior to arrival at the clinic. For PK purposes, NSAI should be administered at the same time (or up to 20 minutes after) the first dose of blinded study drug through Cycle 4, Day 1. Subsequently, the interval between administration of blinded study drug and NSAI may be adjusted based on the judgment of the investigator. For patients in cohort B, on Cycle 2 Day 1, patients will take the blinded study drug at home at least 4 hours prior to arrival at the clinic. For PK purposes, fulvestrant should be administered at the same time as (or up to 20 minutes after) the first dose of blinded study drug, except when specified otherwise in the PK Sampling Schedule ([Attachment 7](#)) through Cycle 4 Day 1. Subsequently, the interval between administration of blinded study drug and fulvestrant may be adjusted based on the judgment of the investigator. Fulvestrant 500 mg should be administered intramuscularly into the buttocks slowly (1 to 2 minutes per injection) as two 250-mg injections, one in each buttock; however, for patients with moderate hepatic impairment (defined as Child-Pugh Class B), including any patient who develops moderate hepatic impairment during study treatment, fulvestrant 250 mg should be administered intramuscularly into the buttock slowly (1 to 2 minutes) as one 250-mg injection.

- r EORTC QLQ-C30, mBPI-sf should be administered twice at baseline (Day -14 to Day -1, and at C1D1), Cycle 2 Day 1, and then on Day 1 of every second cycle beginning with Cycle 3 and continuing through Cycle 13, on Day 1 of every third cycle after Cycle 13, and at Short-Term Follow-Up. Patients should complete these assessments before extensive interaction with site staff.

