### **6.8.2. Quality of Life**

Data from the EORTC QLQ-C30 (Aaronson et al. 1993) instrument will be scored as described by the European Organization for Research and Treatment of Cancer (EORTC) scoring manual (Fayers et al. 2001).

A mixed effects, repeated measures model will be applied to compare treatment arms by cycle with respect to each instrument. The model will include baseline score as a covariate and an unstructured covariance matrix will be utilized. The analysis will include all cycles for which at least 25% of patients in each arm have an assessment.

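### The protocol files the end-of-treatment pain score under the last treatment cycle, but the only such questionnaire scheduled falls about 23 to 37 days after study drug stops.

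*Protocol*

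**What the plan says.** Protocol 12.2.11.2 has two filing rules for the mBPI-sf. For scheduled visits, "the Day 1 score of each subsequent cycle will be attributed to the previous cycle". For the end of treatment, "The mBPI-sf will be administered at treatment discontinuation and grouped with observations from the previous cycle".

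Note r of the Study Schedule (Protocol Attachment 1) lists every questionnaire time: two at baseline, Cycle 2 Day 1, Day 1 of alternate cycles from Cycle 3 to Cycle 13, then "on Day 1 of every third cycle after Cycle 13, and at Short-Term Follow-Up". No questionnaire is listed for the day treatment stops. Under note a, short-term follow-up starts the day after it is agreed that "the patient will no longer continue study drug and lasts approximately 30 days" (±7 days), and its procedures are done once, at the end of that period. Protocol 10.2.1.2 gives the mBPI-sf a 24-hour recall.

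The pain analyses that could use the score are:
- SAP 6.8.1: the proportion of patients whose worst pain rises by at least 2 points at any time on therapy.
- Protocol 12.2.11: maximum change from baseline in worst pain, with no restriction to on-treatment scores.
- Protocol 12.2.11.2: time to worsening, by a 2-point postbaseline rise or a step up in analgesic class. SAP 6.8 does not mention this analysis.
- SAP 6.8.3: a repeated measures model by cycle, limited to cycles where at least 25% of each arm have an assessment. It repeats neither filing rule and does not mention visit 801.

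**The concern.** The filing rule suits a score taken on the day of stopping. The schedule collects no such score, so the rule has either nothing to act on or only the visit 801 score. In the second case, a pain rating from roughly a month after blinded drug stopped is counted as an on-treatment observation.

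Several things can change pain in that month: progression, loss of study drug, new systemic treatment or radiotherapy. The plan foresees new therapy in this window. For best overall response, SAP 6.7.2.3 accepts short-term follow-up assessments only if they precede post-discontinuation therapy, and SAP 6.7.2.4 censors duration of response when such therapy starts. No matching line is drawn for pain.

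At stake is whether the on-therapy pain results describe patients on therapy, and whether two analysts working from these documents would produce the same table.

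**Working it through.** The plan states no figure on this point, so the check sets timing windows against recall periods and then sizes the effect on cycle means by illustration.

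**1. Timing.** Inputs: follow-up of 30 ± 7 days (Study Schedule note a) and 24-hour recall (Protocol 10.2.1.2).
- Earliest visit: 30 − 7 = day 23, recall covering days 22 to 23.
- Latest visit: 30 + 7 = day 37, recall covering days 36 to 37.

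The recall window therefore never reaches a day on blinded drug. If drug was already on hold when the decision was made, the gap is longer.

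**2. Outcomes that one score can decide.** A patient counts for the 2-point outcome if any eligible score is at least 2 above baseline. Adding the visit 801 score can only move her from no to yes. If a fraction f of an arm reaches 2 points at visit 801 and not before, that arm's proportion rises by f. The between-arm change is f(abemaciclib) − f(placebo), and its sign is unknown. Maximum change is exposed in the same way. The documents give nothing from which to estimate f.

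**3. Cycle means (illustration).** Assumptions: exponential PFS, stopping only at progression, Cohort A medians, and every patient who stops supplying a visit 801 score filed to that cycle. Inputs: control median 14.4 months and hazard ratio 0.626 (Protocol 12.1); one month = 365/12 days (SAP 6.1.2).
- Abemaciclib median: 14.4 / 0.626 = 23.0 months, a gain of 8.6 months (59.7%), as the protocol states.
- Probability of stopping in one cycle: p = 1 − exp[−ln 2 × 28 / (median × 365/12)].
- Control p = 4.3%; abemaciclib p = 2.7%.
- If off-drug scores differ from on-drug scores by an assumed 2 points, the arm difference shifts by (0.0274 − 0.0433) × 2 = −0.03 point, or +0.03 if the difference runs the other way.
- With extra abemaciclib stops of fraction e per cycle, p becomes 1 − (1 − 0.0274)(1 − e). For an offset of +2 points, e = 1% gives −0.01 and e = 3% gives +0.03, so the sign reverses.

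**4. Which cycles the score enters.** Day 1 questionnaires at Cycles 2, 3, 5, 7, 9, 11, 13, 16, 19 and so on are attributed to Cycles 1, 2, 4, 6, 8, 10, 12, 15, 18 and so on. A follow-up score filed to Cycle 3, 5, 7, 9, 11, 13, 14, 16, 17, 19, 20, 22 or 23 (13 of the first 24 cycles) has no scheduled score beside it. Only that cycle's stoppers would be there, 3% to 4% in step 3, so the 25% rule would drop the cycle. This assumes that the SAP model follows the protocol's Day 1 attribution, which SAP 6.8.3 does not say.

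**The case against.** The strongest reply is that Protocol 12.2.11.2 never names visit 801. Read literally it describes a score taken on stopping, for which the last cycle is the natural label. The SAP, to which Protocol 12.2.11 defers for details, does not repeat the rule, already restricts the 2-point outcome to on-therapy scores, and has a 25% rule that would remove many affected cycles. Keeping off-drug scores could also serve a treatment-policy aim.

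Part of this stands. The effect on cycle means is probably small, and the use of the visit 801 score is one reading of the text. But the literal reading needs a questionnaire that the schedule does not contain, so the passages disagree either way. The SAP does not say when on-therapy ends, nor does it withdraw the protocol's grouping rule. A treatment-policy aim, which the documents neither state nor exclude, would justify keeping the score but not labelling it as the previous cycle.

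Two stronger readings are tempting.

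**That the QLQ-C30 symptom-burden objective is affected too.** The grouping rule is written for the mBPI-sf alone. SAP 6.8.2 says "A mixed effects, repeated measures model will be applied to compare treatment arms by cycle with respect to each instrument", and no passage assigns an off-drug QLQ-C30 score to a cycle.

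**That questionnaires follow toxicity delays and so hide abemaciclib's symptom cost.** The start of a cycle may move "up to 14 days to allow sufficient time for recovery from toxicity possibly related to a study drug", for the QLQ-C30 "The recall period is the past week", and before blinded drug restarts nonhematologic toxicity "must resolve to either baseline or at least Grade 1". A delayed Day 1 can therefore follow a drug-free week. But this is a permitted case, not the rule:
- Protocol 9.1 defines study treatment as blinded drug and/or NSAI/fulvestrant.
- Table JPBQ.9.2 and Protocol 9.6.5 direct the hold at blinded drug.
- Protocol 9.4.1.1.2 lets NSAI/fulvestrant administration set Day 1 while blinded drug is suspended.
- Protocol 9.4.1.1.4 exempts alopecia and fatigue from the recovery requirement.

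The documents give no frequency of delays by arm, so neither the size nor the existence of a bias is shown.

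**Conclusion.** The concern holds for the mBPI-sf. The protocol's grouping rule and the Study Schedule do not agree. Applied to the only post-treatment questionnaire, the rule labels a score from about day 23 to 37 after the decision to stop study drug as on-treatment, contrary to the on-therapy definition in SAP 6.8.1.

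The 2-point proportion and maximum change are most exposed, by an amount that cannot be sized from the documents. Time to worsening can also turn on one visit 801 score, although its definition is postbaseline rather than on-therapy. The effect on by-cycle means is about 0.03 point on a 0 to 10 scale, direction open, given exponential PFS, the protocol's Cohort A assumptions, an assumed 2-point offset, and up to 3% extra abemaciclib stops per cycle.

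Pain is an exploratory objective. The primary endpoint and the QLQ-C30 objective are untouched, and it is not shown that symptom burden is mis-stated. The point is worth correcting because it is a real inconsistency that is cheap to remove.

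**What to change.** 1. Reconcile Protocol 12.2.11.2 with Study Schedule notes a and r. Either remove the statement that the mBPI-sf is given at discontinuation, or schedule that assessment.
2. In Protocol 12.2.11.2 and SAP 6.8.3, make visit 801 a separate off-treatment time point, not grouped with the previous cycle and not in the by-cycle models.
3. In SAP 6.8.1, define on-therapy by the date of last dose for the 2-point outcome, and say which drug's last dose counts. SAP 6.1.2 uses study drug for abemaciclib or placebo, while Protocol 9.4.1.1.1.1 allows endocrine therapy to continue after blinded drug stops.
4. Report maximum change in worst pain on on-therapy scores.
5. For time to worsening, keep the stated postbaseline definition and add a sensitivity analysis without visit 801 scores. Removing them from the main analysis would discard post-progression pain and could make the censoring informative.
6. Optionally, add a sensitivity analysis excluding scores whose recall window lies wholly within a dose hold.

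The cost is wording in two documents and a little more analysis work. No extra visit or questionnaire is needed unless the sponsor chooses to schedule one at discontinuation.

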### **12.2.11.3. Resource Utilization**

Utilization data will be summarized descriptively by category across arms in a cohort (eg, analgesic use, bisphosphonate use, transfusions, radiation, surgery, and hospitalization days), including a frequency table with tabular statistics. Tests for differences in proportions between treatment groups and between response groups will be performed.

